#### **Secondary objectives**

- Investigation of the effect of a novel formulation of lycopene fused with phosphatidylcholine chaperone on tomographic parameters of liver in NASH patients.
- Evaluation of the effect of a novel formulation of lycopene fused with phosphatidylcholine chaperone on liver specific enzymes including alanine aminotransferase, aspartate aminotransferase, gamma glutamyl transpeptidase, alkaline phosphatase and some others in NASH patients.
- Assessment of the effect of phosphatidylcholine chaperone alone on tomographic parameters of liver and plasma biochemistry values in NASH patients.

## **7.4 Study Design**

### **7.4.1 Selection and randomization of volunteers**

Medical personnel from the outpatient clinic of the Institute of Cardiology, Saratov, Russian Federation will be informed about launching the study, its major goal and selection criteria for volunteers. Suitable individuals will be invited for a preliminary check-up (physical and laboratory investigation) during the initial phase of enrolment. All suitable individuals will be re-screened after the wash-out period of the study before the final decision on study enrolment is made.

Randomization of volunteers in the study will be performed using widely accepted methods such as simple randomization and stratified randomization. Briefly, software containing a random number generator will be applied to the database of volunteers. The assigned group will be considered final. The groups will be balanced according to numerical age and gender with special software.

Stratified randomization will be used to enhance the statistical power of the final results and will ensure equality of groups for secondary selection criteria.

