**Sample Size**

40 subjects divided into two clinical groups, 20 subjects in each group).

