## **13. STATISTICAL METHODS/DATA ANALYSIS**

### **13.1 Study endpoint**

For assessment of normally distributed parameters the Shapiro-Wilk method will be used. Student's t-test will then be applied for both paired and unpaired samples. Between-group differences at one time point will be evaluated by Wilcoxon-Mann-Whitney test (continuous variables) and Fisher's Exact test (categorical variables). Data analysis will be performed using Stata SE, version 12.1. All statistical tests will be two-sided and statistical significance level alpha will be set at 0.05 for the analysis.

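### Section 7.4.1 does not settle on one randomisation method, and the section 13.1 tests ignore age and gender, which the allocation is meant to balance for the sake of power

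*Protocol*

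**What the plan says.** Protocol section 7.4.1 makes five statements about allocation:

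- Methods: "Randomization of volunteers in the study will be performed using widely accepted methods such as simple randomization and stratified randomization".
- Mechanism: "software containing a random number generator will be applied to the database of volunteers".
- Finality: "The assigned group will be considered final".
- Balance: "The groups will be balanced according to numerical age and gender with special software".
- Purpose: "Stratified randomization will be used to enhance the statistical power of the final results and will ensure equality of groups for secondary selection criteria".

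The Sample Size entry of the Protocol Summary plans 40 subjects, with "20 subjects in each group". Section 13.2 plans 80, with 40 per group.

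For the analysis, section 13.1 lists paired and unpaired t-tests and adds that "Between-group differences at one time point will be evaluated by Wilcoxon-Mann-Whitney test" for continuous variables, with Fisher's exact test for categorical ones. None of these has a stratum or covariate term. Section 13.3 allows other methods, but only where the distribution of the data makes the listed ones unsuitable.

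**The concern.** There are two linked problems.

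**Allocation.** Simple and stratified randomisation are alternatives for producing one list. The section offers both as examples, later says that stratification will be used, and never withdraws simple randomisation. The age and gender sentence can be read as a description of the stratification (or of a minimisation), or as a separate operation. Someone asked to generate the list could not tell which is meant, and an analysis plan written later cannot repair an allocation already carried out.

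**Analysis.** The stated reason for stratifying is power. Balancing a prognostic factor removes its contribution from the true variance of the treatment difference. An unadjusted test still counts that contribution in its standard error. The test is then conservative and uses only part of the precision that the design provides. At 20 or 40 per group, that precision is worth having.

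**Working it through.** **1. The plan's own figure.** Section 13.2 gives one-sided 2.5%, 90% power and 40 per group, but no effect or SD, so its sample size cannot be reproduced forwards. Solved backwards with the normal approximation, d = (1.960 + 1.282) × √(2/40) = 0.725 SD. For a t-test with 78 degrees of freedom, 0.735 SD gives 90%. I use 0.735 SD below as an assumption. Two-sided 5% in section 13.1 has the same critical value as one-sided 2.5%.

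**2. Set-up.** The total SD is 1, N is the total sample, and allocation is balanced within four equal strata (gender by age group). The strata explain a share r of outcome variance. The protocol gives no value for r, so I take 10, 20 and 30%, for which √(1−r) = 0.949, 0.894 and 0.837.

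- True standard error of the difference: √(4(1−r)/N).
- Standard error used by the unadjusted t-test: about √(4/N).

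**3. Type I error, unadjusted:** 2 × [1 − Φ(1.96/√(1−r))].

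| r | 1.96/√(1−r) | Type I error |
|---|---|---|
| 10% | 2.066 | 3.9% |
| 20% | 2.191 | 2.8% |
| 30% | 2.343 | 1.9% |

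**4. Power at N = 40.** d√(N/4) = 0.735 × √10 = 2.324. The critical values are 2.024 (38 df, unadjusted) and 2.030 (35 df, adjusted for four strata).

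- Unadjusted: Φ((2.324 − 2.024)/√(1−r))
- Adjusted: Φ(2.324/√(1−r) − 2.030)

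| r | Unadjusted | Adjusted |
|---|---|---|
| 10% | Φ(0.316) = 62% | Φ(0.420) = 66% |
| 20% | Φ(0.335) = 63% | Φ(0.569) = 71–72% |
| 30% | Φ(0.358) = 64% | Φ(0.748) = 77% |

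Simulation of the same set-up agrees to within about one point. At r = 0 the two analyses have practically the same power, about 62%.

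**5. Power at N = 80.** d√(N/4) = 0.735 × √20 = 3.287. The critical values are 1.991 (78 df) and 1.992 (75 df).

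| r | Unadjusted | Adjusted |
|---|---|---|
| 10% | Φ(1.366) = 91% | Φ(1.473) = 93% |
| 20% | Φ(1.449) = 93% | Φ(1.683) = 95% |
| 30% | Φ(1.549) = 94% | Φ(1.937) = 97% |

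**6. Equal split under simple randomisation.**

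- Exactly 20:20 has probability C(40,20)/2⁴⁰ = 12.5%.
- Exactly 40:40 has probability C(80,40)/2⁸⁰ = 8.9%.
- Averaging the power at 0.735 SD over all binomial splits of 40 gives 60.9%, against 62.0% at 20:20. The cost is about one point.

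These calculations are for the t-test. The Wilcoxon-Mann-Whitney test is conservative for the same reason, since its null variance also ignores the strata.

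**The case against.** **The text does choose a method.** The two methods follow the words for giving examples, the section ends by saying that "Stratified randomization will be used to enhance the statistical power of the final results", and section 15.2 requires a master randomisation list. This is fair. The likely intention is stratified allocation, and the defect is one of unclear drafting. But simple randomisation remains named, and the balancing sentence is not tied to the stratification.

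**Subjects moved after assignment.** A reader might infer from the order of the sentences that subjects are to be shifted between groups to correct imbalance, which would undo the randomisation. The text does not support this. It gives no timing for the balancing, and it says "The assigned group will be considered final". What stands is that the protocol should say the balancing is not a later step.

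**Equal groups not delivered.** A reader might also infer that the planned split cannot be reached. That is so only for independent coin tosses. Blocking within strata, or dividing a known list at random, gives equal groups. The split is unassured, and the cost of missing it is small.

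**Stratifying loses power.** It does not, compared with simple randomisation and the same test. At 40 subjects the unadjusted test after stratification has about 62 to 64% power, against about 61% under simple randomisation. The claim of enhanced power is therefore weak but not false, and an error rate below 5% creates no excess of false positives.

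**Adjustment belongs in the analysis plan.** An analysis plan that is not at hand may add it, and block sizes, age bands and who prepares the list are not at issue here. But section 13.1 names the tests, and the exception in section 13.3 is worded for distributional reasons, so the protocol as written does not match its own rationale.

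**Conclusion.** The point holds in a limited form. Section 7.4.1 leaves open which method produces the allocation and whether the age and gender balancing is part of it. Its power rationale does not match the tests in section 13.1.

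The size depends on how well age and gender predict the outcome, for which the protocol gives no figure:

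- At 40 subjects, adjustment adds about 4, 8 or 13 points of power for assumed shares of 10, 20 or 30%. The unadjusted test keeps only 1 to 3 points over simple randomisation, so most of the available gain is forgone.
- At 80 subjects, where power is already high, adjustment adds about 2 to 4 points.
- At a share of 0%, nothing is lost.

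The low power at 40 subjects should not be put down to the randomisation. It comes from applying the effect detectable with 80 to half that number. The conflict between 40 and 80 subjects is a separate issue with a larger effect on power. The documents do not show broken randomisation, an unattainable split or an inflated error rate. The change is worth making because it costs almost nothing.

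**What to change.** **Section 7.4.1.** Name one method: stratified allocation by gender and age group. Delete the reference to simple randomisation. Replace the separate balancing sentence with a statement that balance on gender and age is achieved through the allocation itself and that nothing is changed after assignment. Name these factors in place of the unspecified secondary selection criteria, so that the factors balanced and the factors analysed are the same.

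**Section 13.** Make the primary between-group comparison a linear model with terms for treatment, gender and age, the factors used in the allocation. The listed unadjusted tests can stay as supporting analyses.

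**Cost.** The allocation wording must be settled before the list is generated, and the analysis wording before unblinding. The model uses a few degrees of freedom (35 instead of 38 at 40 subjects with four strata). It needs no extra subjects, visits or data, since age and gender must be known for the allocation anyway.

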#### **7.4.2 Schedule of Procedures/Evaluations**

1. 2 months prior to study initiation. (Initial enrolment with preliminary physical and laboratory investigation).
2. 2 – 5 days prior to study initiation. Final qualifying physical and laboratory investigation.
3. Day "0" of the study. Physical and laboratory investigation to obtain baseline clinical and laboratory values. Computed tomography.
4. End of the 2nd and 4th months of the study. Physical and laboratory investigation to obtain mid-point clinical and laboratory values.
5. End of the 6th month of the study. Concluding physical and laboratory investigation to obtain final clinical and laboratory values. Computed tomography.

#### **7.4.3 Study Duration**

Interventional period is designed to last for 6 months. Enrolment period and search for volunteers may take up to 2 months.

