**Study Design**

The study is designed as a double-blinded, interventional, randomized clinical study involving patients with NASH. A major research question is whether ingestion of lycopene stabilized with Lycosome™ formulated phosphatidylcholine chaperone can reverse clinical and laboratory manifestations of NASH. Therefore, the primary endpoint of the project is the size of the liver and parameters reflecting lipid accumulation in the hepatic tissue at the end of the interventional period. Changes in the activity of liver-specific enzymes and parameters of lipid homeostasis represent the secondary question since normalization of serum levels of hepatic enzymes represents another important criterion of liver damage and its reversal in NASH. Biochemical parameters in serum specimens will be investigated before commencing the study, at the intermediate time points of 1 month and in the end of the study after 2 months treatment. To assess changed in the liver span Ultrasonography was used before and in the end of the trial.

Subjects will be assigned to take orally once a day either capsules containing 450 mg of regular phosphatidylcholine or 450 mg of the same phospholipid in Lycosome™ formulation with 7 mg of lycopene (Cambridge, UK).

The formulations will be dispensed to the subjects during follow-up visits each month. Monthly visits are planned to determine compliance and adherence to the protocol. A basic medical check-up will be performed and subjects will be asked questions to determine adherence to the protocol during each visit.

Packaging and labeling of the study products will be carried out according to the guidelines of NIH and US Department of Health and Human Services as recommended for biologics and investigational health food products. The formulations will be shipped to the study site in specially designed containers with primary and secondary components. The container closure system will prevent exposure of the investigational products to light, moisture, temperature extremes and air. This packaging system guarantees stability of the product for intended use. Protection from microbial contamination will be provided by maintaining container integrity after the packaging system is sealed. An adequate and validated procedure was used for investigational product manufacture and packaging.

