All individual packages will be labeled with a numerical code. None of the volunteers or trial personnel will be informed of study group assignment for the duration of the study. Unblinding of the results is planned to be performed by an independent statistician who will be hired and assigned to the work at the end of the study period.

Upon arrival at the clinical site the study products will be inspected by the Medical Officer and Clinical Monitor, then placed in a locked room at the clinic. Only the Medical Officer, PI and Clinical Monitor will have access to the products during the study period. Each subject will be given a one month supply of the study product at the "zero" time point of the study and then subsequently for each month of the study period following verification of compliance with the study protocol.

Total study duration is six months with a medical check-up for each volunteer at the "0" time point of the study as well as at 1st month and at the 2nd, the end of the interventional period.

During the medical check-ups each volunteer will be subjected to thorough clinical and laboratory investigation. Clinical investigation will include reading the vital signs, determination of body mass index, anthropometry, blood pressure measurement and computed tomography (at the initial and final time points of the study). Among laboratory tests will be determination of fasting serum glucose and lipids (total cholesterol, LDL, HDL and total triglyceride

[figure not shown]

levels), determination of ALT and AST levels, alkaline phosphatase, gamma glutamyl transpeptidase, lactate dehydrogenase, total bilirubin, CRP, LDL oxidation and IOD. Moreover, serum lycopene concentration and lycopene isomer profile will be measured at the initial and final points of the interventional period. All volunteers will also be subject to a standard hematological investigation.

Results collected for each volunteer will be stored as both paper files and digital files in Excel format and will be available for access by the Medical Officer, Medical Monitor and PI. To avoid any bias each subject will be given a random computer code containing three numerical characters and three letters. Decoding of the individual results will be carried out by an independent statistician hired for the purpose.

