#### **7.4.6 Formulations and Mode of Intake**

Subjects will be assigned to take orally twice a day either Lycosome™ formulated phosphatidylcholine chaperone, an essential phospholipid formulation containing 450 mg of phosphatidylcholine, or Lycosome™ formulated phosphatidylcholine chaperone (450 mg) fused with lycopene (7mg), an essential carotenoid. The latter is a novel lycosome formulation of lycopene with enhanced bioavailability developed by Lycotec Ltd (Cambridge, UK). Both formulations will be taken orally, twice a day (morning and evening) for a period of 6 months. The volunteers will be asked to take the study products twice a day after meals.

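### The protocol defines the intervention in two incompatible ways (once daily to month 2, or twice daily to month 6), so the primary endpoint falls at either month 2 or month 6

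*Protocol*

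**What the plan says.** Two descriptions of the intervention stand side by side in the current text.

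**Protocol Summary, Study Design.** On frequency: "Subjects will be assigned to take orally once a day". Serum parameters are taken before the start, then "at the intermediate time points of 1 month and in the end of the study after 2 months treatment". A later paragraph repeats the end point, placing check-ups at time zero, the first "month and at the 2 nd , the end of the interventional period". CT is planned at the initial and final time points. The primary endpoint (liver size and measures of hepatic fat) is attached to the close of the intervention, and no month is given.

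**Section 7, Clinical Protocol.** Section 7.4.3: "Interventional period is designed to last for 6 months". Section 7.4.6: "Both formulations will be taken orally, twice a day (morning and evening) for a period of 6 months". Section 7.4.2 places CT at day 0, treats months 2 and 4 as mid-point visits with physical and laboratory work only, and puts this at month 6, together with the second CT: "Concluding physical and laboratory investigation to obtain final clinical and laboratory values".

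Section 11 adds that liver size is measured at intermediate and final points of the intervention, again without naming months.

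**The concern.** Duration and frequency define the treatment being compared, and the close of the intervention defines when the primary endpoint is read. If the protocol carries two versions of both, it does not say which treatment effect the trial estimates. An effect on liver size after 2 months of once-daily intake and one after 6 months of twice-daily intake are different quantities, and a result for one does not answer the question for the other.

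The conflict also reaches data collection. Under section 7.4.2 no CT is done at month 2, so a reader who takes the Summary's end of treatment would find no second CT at the time of the primary endpoint. Under the Summary the last visit is at month 2, so a reader who takes section 7.4.3 would find no assessment at the time of the primary endpoint at all. An analysis plan can name a visit, but it cannot settle what subjects take or when the last scan is done.

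**Working it through.** **Step 1: the two versions compared.**

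| Item | Protocol Summary, Study Design | Sections 7.4.2, 7.4.3, 7.4.6 |
|---|---|---|
| Intake frequency | once daily | twice daily (7.4.6) |
| Intervention ends | month 2 (stated twice) | month 6 (7.4.3, 7.4.6; concluding visit in 7.4.2) |
| Assessments | 0, 1, 2 months | 0, 2, 4, 6 months (7.4.2) |
| Final CT | final time point, so month 2 | month 6 (7.4.2) |
| Status of month 2 | final visit | mid-point visit, no CT |
| Primary endpoint falls at | month 2 | month 6 |

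**Step 2: could this be total duration against treatment duration?** The Summary does give a six-month total: "Total study duration is six months with a medical check-up for each volunteer". But the same sentence ends the intervention at month 2, while 7.4.3 gives 6 months for the intervention and 7.4.6 gives 6 months for the intake itself. Both sides describe the same period, so the distinction does not remove the conflict.

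**Step 3: difference in planned exposure.** Inputs: 450 mg phosphatidylcholine and 7 mg lycopene (lycopene arm; Study Design and 7.4.6), with the frequencies and durations above. Assumption: 30-day months.

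Intakes = months × 30 × intakes per day.

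- Summary: 2 × 30 × 1 = 60
- Section 7: 6 × 30 × 2 = 360
- Mixed readings: 2 × 30 × 2 = 120 and 6 × 30 × 1 = 180

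Section 7.4.6 does not say whether 450 mg / 7 mg is per intake or per day, so both readings are shown.

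| Reading of 7.4.6 | Summary | Section 7 | Ratio |
|---|---|---|---|
| Per intake | 60 × 450 mg = 27 g; 60 × 7 mg = 420 mg | 360 × 450 mg = 162 g; 360 × 7 mg = 2,520 mg | 6 |
| Per day | 27 g; 420 mg | 180 × 450 mg = 81 g; 180 × 7 mg = 1,260 mg | 3 |

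**Step 4: difference in endpoint time.** Month 6 − month 2 = 4 months; 6 / 2 = a three-fold difference in follow-up to the primary reading.

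**The case against.** The strongest reply is that the endpoint does have a time. It is read when the intervention ends, so once the duration is settled the month follows, and the visit label may sit in an analysis plan that is not shown. That is fair as far as it goes: the silence of section 13.1 on the month is not a separate defect. It does not help with the duration, which only the protocol can fix.

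Four stronger readings are tempting, but the documents do not support them.

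- **Inflated false-positive rate.** A reader might infer two looks, at months 2 and 6, and a rate of 1 − 0.95² = 9.75%. That figure assumes independent tests, whereas these would be repeated readings on the same subjects. More importantly, no imaging schedule gives the primary measure at both months. Only section 11 mentions an intermediate liver-size reading, without a month.
- **Supply that does not match the visits.** The Summary provides that "Each subject will be given a one month supply of the study product" at the start and for each later month, while 7.4.2 lists investigations every second month. But 7.4.2 does not list dispensing, so monthly dispensing visits can coexist with it.
- **A six-month total as a contradiction in itself.** Enrolment may take up to 2 months, and total study time need not equal treatment time. A six-month total around a shorter intervention is possible.
- **Different treatment within one arm.** The protocol describes one clinic with controlled dispensing. Divergence between subjects is possible but not shown.

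**Conclusion.** The contradiction is real and must be resolved before the trial can have one stated treatment and one primary time point. The accurate description is that the intervention is defined in two incompatible ways, rather than left undefined. The month-2 version appears twice in the Summary and the month-6 version in three subsections of section 7, so it is not a single slip of the pen.

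The primary endpoint moves by 4 months between versions. Planned cumulative exposure differs six-fold if the amounts in 7.4.6 are per intake and three-fold, from duration alone, if they are daily totals. Both ratios rest on 30-day months and full intake. No claim about the size of any type I error inflation follows from these documents. Nothing here judges which regimen or duration is right.

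**What to change.** Reconcile the Study Design text of the Protocol Summary with sections 7.4.2, 7.4.3 and 7.4.6, and align the liver-size timing in section 11, so that the protocol states:

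- one intake frequency, with the amount given explicitly per intake or per day;
- one interventional period;
- one visit schedule;
- one final imaging time.

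Then name that single end-of-intervention visit as the time of the primary endpoint. The choice of regimen and duration belongs to the clinical team.

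The cost is a protocol amendment with ethics approval (section 16.1) and, if subjects are already enrolled, renewed consent where the change is substantial (section 16.3). Whether visits, product or imaging change in number depends on which version is kept.
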